### **8.3.3 Pharmacokinetics and Drug Metabolism**

Cetuximab administered as monotherapy or in combination with concomitant chemotherapy or radiation therapy exhibits nonlinear pharmacokinetics. The area under the concentration time curve (AUC) increased in a greater than dose proportional manner while clearance of cetuximab decreased from 0.08 to 0.02 L/h/m^2 as the dose increased from 20 to 200 mg/m^2, and at doses >200 mg/m^2, it appeared to plateau. The volume of the distribution for cetuximab appeared to be independent of dose and approximated the vascular space of 2–3 L/m^2.

Following the recommended dose regimen (400 mg/m^2 initial dose; 250 mg/m^2 weekly dose), concentrations of cetuximab reached steady-state levels by the third weekly infusion with mean peak and trough concentrations across studies ranging from 168 to 235 and 41 to 85 µg/mL, respectively. The mean half-life of cetuximab was approximately 112 hours (range 63–230 hours). The pharmacokinetics of cetuximab were similar in patients with HNSCC and those with colorectal cancer. Based on a population pharmacokinetic analysis, female patients with colorectal cancer had a 25% lower intrinsic clearance of cetuximab than male patients. Qualitatively similar, but smaller gender differences in cetuximab clearance were observed in patients with HNSCC. The gender differences in clearance do not necessitate any alteration of dosing because of a similar safety profile.

### **8.3.4 Supplier**

Cetuximab is commercially available and is listed in the compendia as indicated for the therapy of HNSCC.

### **8.3.5 Dosage Form**

Each single-use, ready to use 50-mL vial contains 100 mg of cetuximab at a concentration of 2 mg/mL and is formulated in a preservative-free solution containing 8.48 mg/mL sodium chloride, 1.88 mg/mL sodium phosphate dibasic heptahydrate, 0.42mg/mL sodium phosphate monobasic monohydrate, and Water for injection, USP.

### **8.3.6 Storage and Stability**

Cetuximab should be stored in a secure area according to local regulations. Store vials under refrigeration at 2° C to 8° C (36° F to 46° F). DO NOT FREEZE. Increased particulate formation may occur at temperatures at or below 0°C. This product contains no preservatives. Preparations of cetuximab in infusion containers are chemically and physically stable for up to 12 hours at 2° C to 8° C (36° F to 46° F) or up to 8 hours at controlled room temperature (20° C to 25° C; 68° F to 77° F).

Discard any remaining solution in the infusion container after 8 hours at controlled room temperature or after 12 hours at 2° to 8° C. Discard any unused portion of the vial.

### **8.3.7 Safety Precautions**

Appropriate mask, protective clothing, eye protection, gloves, and Class II vertical-laminar-airflow safety cabinets are recommended during preparation and handling. Opened vials must be disposed of at the investigational center as chemotherapy or biohazardous waste provided documented procedures for destruction are in place.

Cetuximab therapy should be used with caution in patients with known hypersensitivity to cetuximab, murine proteins, or any component of this product. It is recommended that patients wear sunscreen and hats and limit sun exposure while receiving cetuximab as sunlight can exacerbate any skin reactions that may occur.

### **8.3.8 Premedication**

In an effort to prevent a hypersensitivity reaction, all patients should be premedicated with diphenhydramine hydrochloride 50 mg (or an equivalent antihistamine) IVPB given at least 30 minutes prior to the cetuximab. Premedication will also include 1Liter normal saline, hydrocortisone 100 mg IVPB and albuterol inhalation (by nebulizer or inhaler) according to standard of care procedures.

### **8.3.9 Preparation and Administration**

Cetuximab must not be administered as an IV push or bolus. Cetuximab must be administered with the use of a low protein binding 0.22-micrometer in-line filter. Cetuximab is supplied as a 50-mL, single-use vial containing 100 mg of cetuximab at a concentration of 2 mg/mL in phosphate buffered saline. DO NOT SHAKE OR DILUTE.

Cetuximab can be administered via infusion pump.

#### **Infusion Pump:**

- Draw up the volume of a vial using a sterile syringe attached to an appropriate needle (a vented spike or other appropriate transfer device may be used).
- Fill cetuximab into a sterile evacuated container or bag such as glass containers, polyolefin bags (e.g., Baxter Intravia), ethylene vinyl acetate bags (e.g., Baxter Clintec), DEHP plasticized PVC bags (e.g., Abbott Lifecare), or PVC bags.
- Repeat procedure until the calculated volume has been put in to the container. Use a new needle for each vial.
- Administer through a low protein binding 0.22-micrometer in-line filter (placed as proximal to the patient as practical).

- Affix the infusion line and prime it with cetuximab before starting the infusion.
- Maximum infusion rate should not exceed 5 mL/min.
- Use 0.9% saline solution to flush line at the end of infusion.
- The infusion rate of cetuximab must never exceed 10 mg/minute (5 mL/min). The infusion time of cetuximab should not exceed 4 hours. Patients must be continuously observed during the infusion for signs of anaphylaxis.

### **8.3.10 Patient Monitoring**

Patients should be closely monitored for treatment-related adverse events, especially hypersensitivity reactions during the infusion and for one post-infusion observation hour. Vital signs (blood pressure, heart rate, and temperature) will be monitored and recorded prior to the administration of cetuximab, 1/2 hour into the infusion, at the completion of the infusion, and 1 hour post-infusion for the initial dose. During all subsequent administrations of cetuximab, vital signs will be monitored and recorded prior to administration of cetuximab and at the end of the infusion; however, it is recommended that the patient be observed for 1-hour post infusion.

## **9.0 CORRELATIVE STUDIES**

### **9.1 Tumor Biopsy**

Tumor biopsies (core or excisional/incisional) will be used to perform whole exome sequencing (WES), RNAseq, p16INK4a expression, Ki-67 by IHC, total and phospho-Rb by IHC, Cyclin D1 by IHC, Cyclin E by IHC, Cyclin A by IHC, p53 by IHC, p21 by IHC, p27 by IHC, and TUNEL assay. Reverse phase protein array (RPPA) will be performed. RPPA is a high-throughput antibody-based technique developed for Functional Proteomics studies to evaluate protein activities in signaling networks. Additional analyses of other potential biomarkers may be performed as they emerge from the scientific understanding of palbociclib activity. If a biopsy is not feasible for financial reasons or safety concerns, at the Primary Investigator's discretion, the biopsy may be foregone.

#### **9.1.1 Collection of Specimens**

Tumor tissue will be collected at baseline and then after two cycles of neoadjuvant palbociclib monotherapy (conclusion of Step One). It should be collected from the primary tumor site if possible, but involved neck nodal tumor tissue is an alternative. If possible, the same site should be biopsied at baseline and end of C2.

The biopsy should consist of a minimum of 4 needle cores (14-18 gauge is preferred) if neck nodal tissue or 2 small (each 4 x 4 x4 mm) pieces of tumor if primary tumor site tissue.

If the patient has been previously enrolled in Washington University's TAP protocol (head and neck bank, HRPO #201102323), tissue that has been banked may be accessed in lieu of fresh biopsy at baseline.

### **9.1.2 Handling of Specimen(s)**

Tissue should be delivered on saline to the Siteman Cancer Center Tissue Procurement Core within 30 minutes of collection.

## **9.2 Peripheral Blood**

Peripheral blood will be stored to serve as normal DNA comparisons to tumor DNA. It will also be used in an exploratory fashion to look for immunologic changes.

### **9.2.1 Collection of Specimen**

Thirty mL of peripheral blood will be collected into 3 green top tubes at baseline, Cycle 1 D22 of neoadjuvant treatment, Cycle 2 D 22 of neoadjuvant treatment, Cycle 1 D22 of adjuvant treatment, and four months post completion of adjuvant treatment.

### **9.2.2 Handling of Specimen(s)**

Deliver to the SCC Tissue Procurement Core within 30 minutes of collection.

## **9.3 QOLs**

Quality of life will be assessed by administration of the EORTC QLQ-C30 (Appendix D) and the FACT H&N (Appendix E) at the following time points:

- Baseline
- Step One Cycle 2 Day 22
- Day 1 of RT
- Day 35 of RT
- 8-10 weeks after completion of CRT
- Cycle 1 Day 1 (adjuvant)
- Cycle 4 Day 1 (adjuvant)
- EOT (adjuvant)
- 8 months after completion of CRT
- 12 months after completion of CRT
- 18 months after completion of CRT
- 24 months after completion of CRT
- 30 months after completion of CRT
- 36 months after completion of CRT
- 42 months after completion of CRT
- 48 months after completion of CRT

- 54 months after completion of CRT
- 60 months after completion of CRT

## 10.0 STUDY CALENDAR

### 10.1 Induction Palbociclib Monotherapy – Step One

	Baseline 	Step 1 – Cycle 1				Step 1 – Cycle 2				Definitive Chemotherapy/Radiation
		D1	D8	D15	D22	D1	D8	D15	D22	
Palbociclib administration 		X 	X 	X 		X 	X 	X 		
PE w/ECOG PS	X	X		X	X	X			X	
CBC	X	X	X	X	X	X	X	X	X	
CMP + magnesium	X									
PT/INR, PTT	X									
Neck CT w/contrast	X								X 	
FDG-PET/CT	X									
Laryngoscopy w/biopsy 	X									X
EKG	X					X				
Pregnancy test 	X									
FACT-H&N, EORTC QLQ-C30	X								X	
Blood for genomic sequencing	X			X				X		
Rad Tx Planning					X					See Study Calendar 2
Primary Site Photographs	X								X	

1. Palbociclib po 125 mg/day, Days 1-21 of a 28 day cycle.

2. Tumor biopsy specimens (punch, incisional or core needle) will be obtained from PTS or neck nodes. P16 to be tested by IHC and/or HPV-HR ISH at baseline only. Assessment of primary tumor site will be done by laryngoscopy performed in the office or operating room. If the patient has been previously enrolled in Washington University's TAP protocol (head and neck bank, HRPO #201102323), tissue that has been banked may be accessed in lieu of fresh biopsy at baseline.

3. In women of childbearing potential only.

4. Baseline assessments must take place no more than 28 days prior to enrollment.

5. To occur anytime post treatment D21-D25 (for M, 26 for W and 27 for Th patients).

## 10.2 Definitive Chemoradiation (CRT) and Adjuvant Palbociclib - Steps Two and Three

	Step 2						Short Term Follow-up (weeks) 		Step 3						Post Step 3 	Long-Term Follow-Up												
	Definitive CRT (weeks)								Adjuvant Palbociclib 							Months post-end of CRT 												
	0	1	2	3	4	5	6	8-10	14-18	1	2	3	4	5	6	8	12	18	24	30	36	42	48	54	60			
Cohort 1: Cisplatin 	X			X																								
Cohort 2: Cetuximab 	X	X	X	X	X	X	X																					
Accelerated IMRT 	X	-----	X																									
Palbociclib 										X 																		
PE w/palpation	X	X	X		X	X	X	X 	X	X	X	X	X	X	X	X	X	X	X	X	X	X	X	X	X	X		
CBC	X	X	X		X	X		X		X	X	X	X	X	X	X												
CMP + magnesium	X	X		X				X		X	X	X	X	X	X	X												
BMP + magnesium			X		X																							
Neck CT w/contrast								X				X 			X 		X	X	X	X	X	X	X	X	X	X	X	
FDG-PET/CT									X																			
Laryngoscopy								X				X 			X 		X	X	X 									
EKG	X								X 			X 		X 		X												
FACT-H&N	X				X	X			X			X		X			X	X	X	X	X	X	X	X	X	X	X	
EORTC QLQ-C30	X				X	X			X			X		X			X	X	X	X	X	X	X	X	X	X	X	
Primary Site Photographs								X																				
Blood for genomic sequencing									X 							X 												

1. Cisplatin 100mg/m^2 D1, D22. IV Fluids D2-3, D23-24. Sites standard premedication(s) prior to each administration.
2. Delivered once per day M-Th with a boost of 2 treatments at least 6 hours apart on Friday
3. Assessment of primary tumor site will be done by laryngoscopy performed in the office or operating room. To occur 8 months post CRT.
4. Weekly until adequate recovery from CRT toxicities (per physician discretion)
5. Palbociclib po 125 mg/day, Days 1-21 of a 28 day cycle
6. To occur 8 months post CRT. CT of Neck AND Chest
7. Cetuximab 400mg/m^2 D-7, 250 mg/m^2 D1, 8, 15, 22, 29, 36. Sites standard premedication(s) prior to each administration. Week 0 (D -7) applies to cohort 2 only.
8. C1D1, C4D1, C6D29
9. Starting 16-22 weeks post CRT
10. 30-45 days after final cycle of adjuvant palbociclib
11. +/- 1 month
12. After completion of CRT
13. To be collected at Step 3 Cycle 1 D22 and at 4 months post Step 3 (see protocol section 9.2)

14. Laryngoscopy (FOE) will be conducted as standard of care after 12 months of follow-up, so they will occur at some, but not all, of the long-term follow-up visits

## 11.0 DATA AND SAFETY MONITORING

In compliance with the Washington University Institutional Data and Safety Monitoring Plan, the Principal Investigator will provide a Data and Safety Monitoring (DSM) report to the Washington University Quality Assurance and Safety Monitoring Committee (QASMC) semi-annually beginning six months after accrual has opened (if at least one patient has been enrolled) or one year after accrual has opened (if no patients have been enrolled at the six-month mark).

For phase I dose escalation studies, the Principal Investigator will review all patient data at least monthly (or before each dose-escalation if occurring sooner than monthly), and provide a semi-annual report to the Quality Assurance and Safety Monitoring Committee (QASMC). For phase II or dose expansion cohorts of a phase I study, the Principal Investigator will review all patient data at least every six months, and provide a semi-annual report to the QASMC. This report will include:

- HRPO protocol number, protocol title, Principal Investigator name, data coordinator name, regulatory coordinator name, and statistician
- Date of initial HRPO approval, date of most recent consent HRPO approval/revision, date of HRPO expiration, date of most recent audit, study status, and phase of study
- History of study including summary of substantive amendments; summary of accrual suspensions including start/stop dates and reason; and summary of protocol exceptions, error, or breach of confidentiality including start/stop dates and reason
- Study-wide target accrual and study-wide actual accrual
- Protocol activation date
- Average rate of accrual observed in year 1, year 2, and subsequent years
- Expected accrual end date and accrual by cohort
- Objectives of protocol with supporting data and list the number of participants who have met each objective
- Measures of efficacy (phase I studies only if efficacy is objective of the protocol)
- Early stopping rules with supporting data and list the number of participants who have met the early stopping rules
- Power analysis and/or interim analysis (if described in the protocol)
- Summary of toxicities separated by cohorts with the number of dose-limiting toxicities indicated
- Abstract submissions/publications
- Summary of any recent literature that may affect the safety or ethics of the study

The study principal investigator and Research Patient Coordinator will monitor for serious toxicities on an ongoing basis. Once the principal investigator or Research Patient Coordinator becomes aware of an adverse event, the AE will be reported to the HRPO and QASMC according to institutional guidelines.

## 12.0 DATA SUBMISSION SCHEDULE

Case report forms with appropriate source documentation will be completed according to the schedule listed in this section.

Case Report Form	Submission Schedule
Original Consent Form	Prior to registration
On-Study Form	
Cohort Assignment Form	
Research Blood Form	Baseline
PEG Tube Tracker	
Trach Tube Tracker	
Weight Form	Continuous
Toxicity Form	
Step 1 Treatment Form	End of each cycle during Step 1
Step 2 Treatment Form	End of Step 2
Step 3 Treatment Form	End of each cycle during Step 3
MEDWATCH Form	Refer to Section 7.0
Visual Response Form	As needed
FOE or mDLx Form	Baseline Between Day 18 & 22 of Step One Cycle 2 8-10 Week Follow-up 8, 12, 18, 24, 30, 36, 42, 48, 54, and 60 months after completion of CRT
FACT-H&N Form and QLQ-C30 Form	Baseline Step One Cycle 2 Day 22 Day 1 and 36 of RT 8-10 week Follow-up Cycle 1 Day 1 and Cycle 4 Day 1 (adjuvant) EOT (adjuvant) 8, 12, 18, 24, 30, 36, 42, 48, 54, and 60 months after completion of CRT
RECIST Form	Baseline Step One Cycle 2 Day 22 8-10 Week Follow-up 8, 12, 18, 24, 30, 36, 42, 48, 54, and 60 months after completion of CRT
Follow Up Form	8, 12, 18, 24, 30, 36, 42, 48, 54, and 60 months after completion of CRT
Death Form	Time of death

## 12.1 Adverse Event Collection in the Case Report Forms

All adverse events that occur beginning with start of treatment must be captured in the Toxicity Form.

Participant death due to disease progression should be reported on the Toxicity Form as grade 5 disease progression. If death is due to an AE (e.g. cardiac disorders: cardiac arrest),

report as a grade 5 event under that AE. Participant death must also be recorded on the Death Form.

## 13.0 MEASUREMENT OF EFFECT

### 13.1 Antitumor Effect – Solid Tumors

For the purposes of this study, patients should be re-evaluated for response every 8 weeks. In addition to a baseline scan, confirmatory scans should also be obtained not less than 4 weeks following initial documentation of objective response.

Response and progression will be evaluated in this study using the new international criteria proposed by the revised Response Evaluation Criteria in Solid Tumors (RECIST) guideline (version 1.1) [Eur J Ca 45:228-247, 2009]. Changes in the largest diameter (unidimensional measurement) of the tumor lesions and the shortest diameter in the case of malignant lymph nodes are used in the RECIST criteria.

### 13.2 Disease Parameters

**Measurable disease:** Measurable lesions are defined as those that can be accurately measured in at least one dimension (longest diameter to be recorded) as >20 mm by chest x-ray, as >10 mm with CT scan, or >10 mm with calipers by clinical exam. All tumor measurements must be recorded in millimeters (or decimal fractions of centimeters).

**Malignant lymph nodes:** To be considered pathologically enlarged and measurable, a lymph node must be >15 mm in short axis when assessed by CT scan (CT scan slice thickness recommended to be no greater than 5 mm). At baseline and in follow-up, only the short axis will be measured and followed.

**Non-measurable disease:** All other lesions (or sites of disease), including small lesions (longest diameter <10 mm or pathological lymph nodes with  $\geq 10$  to <15 mm short axis), are considered non-measurable disease. Bone lesions, leptomeningeal disease, ascites, pleural/pericardial effusions, lymphangitis cutis/pulmonitis, inflammatory breast disease, and abdominal masses (not followed by CT or MRI), are considered as non-measurable.

*Note: Cystic lesions that meet the criteria for radiographically defined simple cysts should not be considered as malignant lesions (neither measurable nor non-measurable) since they are, by definition, simple cysts.*

‘Cystic lesions’ thought to represent cystic metastases can be considered as measurable lesions, if they meet the definition of measurability described above. However, if non-cystic lesions are present in the same patient, these are preferred for selection as target lesions.

**Target lesions:** All measurable lesions up to a maximum of 2 lesions per organ and 5 lesions in total, representative of all involved organs, should be identified as target lesions

and recorded and measured at baseline. Target lesions should be selected on the basis of their size (lesions with the longest diameter), be representative of all involved organs, but in addition should be those that lend themselves to reproducible repeated measurements. It may be the case that, on occasion, the largest lesion does not lend itself to reproducible measurement in which circumstance the next largest lesion which can be measured reproducibly should be selected. A sum of the diameters (longest for non-nodal lesions, short axis for nodal lesions) for all target lesions will be calculated and reported as the baseline sum diameters. If lymph nodes are to be included in the sum, then only the short axis is added into the sum. The baseline sum diameters will be used as reference to further characterize any objective tumor regression in the measurable dimension of the disease.

**Non-target lesions:** All other lesions (or sites of disease) including any measurable lesions over and above the 5 target lesions should be identified as non-target lesions and should also be recorded at baseline. Measurements of these lesions are not required, but the presence, absence, or in rare cases unequivocal progression of each should be noted throughout follow-up.

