# **3.0 PATIENT SELECTION**

## **3.1 Inclusion Criteria**

1. Larynx SCC, hypopharynx SCC, or oral cavity SCC. HPV-unrelated OPSCC [defined as p16INK4a negative by IHC (staining in < 70% of cells) or HPV High Risk (Type 16 or 18) negative by ISH]. P16INK4a positive larynx SCC, hypopharynx SCC, and oral cavity SCC are eligible given the unknown effect of this on the biology of SCC of these subsites.
2. Overall Stage III, IVA, or IVB disease per AJCC version 7.0.
3. Measurable disease defined as lesions that can be accurately measured in at least one dimension (longest diameter to be recorded) as  $\geq 10$  mm with CT scan, as  $\geq 20$  mm by chest x-ray, or  $\geq 10$  mm with calipers by clinical exam.
4. At least 18 years of age.
5. Normal bone marrow function as defined below:
  - a. Absolute neutrophil count  $\geq 1,000/\text{mcL}$
  - b. Platelets  $\geq 100,000/\text{mcL}$
  - c. Hemoglobin  $\geq 9.0 \text{ g/dL}$
6. QTc  $< 500$  msec by Fridericia
7. Women of childbearing potential and men must agree to use adequate contraception (hormonal or barrier method of birth control, abstinence) prior to study entry, for the duration of study participation, and for 90 days after completion of treatment. Should

- a woman become pregnant or suspect she is pregnant while participating in this study, she must inform her treating physician immediately.
8. Ability to understand and willingness to sign an IRB approved written informed consent document (or that of legally authorized representative, if applicable).

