## **3.2 Exclusion Criteria**

1. Diagnosis of cutaneous, paranasal sinus, salivary, or nasopharynx SCC, or diagnosis of neck nodes with unknown primary.
2. Diagnosis of P16/HPV-ISH positive OPSCC.
3. Presence of distant metastatic disease.
4. Prior systemic therapy for current diagnosis of HNSCC.
5. A history of other malignancy  $\leq 2$  years previous with the exception of basal cell or squamous cell carcinoma of the skin which were treated with local resection only or low risk/curatively treated prostate, thyroid, and cervical cancers.
6. Currently receiving any other investigational agents.
7. Treated within the last 7 days prior to Day 1 of protocol therapy with:

- a. Food or drugs that are known to be STRONG CYP3A4 inhibitors (e.g. grapefruit juice, verapamil, ketoconazole, miconazole, itraconazole, erythromycin, clarithromycin, telithromycin, indinavir, ritonavir, nelfinavir, atazanavir, amprenavir, nefazodone, diltiazem, and delavirdine) or inducers (e.g. glucocorticoids, progesterone, rifampin, phenobarbital, St. John's wort) [moderate CYP3A4 inhibitors/inducers are okay]
  - b. Drugs that are known to prolong the QT interval
  - c. Drugs that are proton pump inhibitors
8. A history of allergic reactions attributed to compounds of similar chemical or biologic composition to palbociclib, cisplatin (for Cohort 1), or cetuximab (for Cohort 2).
9. Uncontrolled intercurrent illness including, but not limited to, ongoing or active infection, symptomatic congestive heart failure, unstable angina pectoris, cardiac arrhythmia, or uncontrolled electrolyte disorders that can compound the effects of a QTc-prolonging drug (e.g. hypocalcemia, hypokalemia, hypomagnesemia).
10. History of cirrhosis.
11. History of renal or liver transplant.
12. Pregnant and/or breastfeeding. Women of childbearing potential must have a negative serum pregnancy test within 28 days of study entry. Female patients must be surgically sterile or be postmenopausal, or must agree to use effective contraception during the period of the trial and for at least 90 days after completion of treatment.
13. Known HIV-positivity and on combination antiretroviral therapy because of the potential for pharmacokinetic interactions with palbociclib. In addition, these patients are at increased risk of lethal infections when treated with marrow-suppressive therapy.

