### 13.3 Methods for Evaluation of Measurable Disease

All measurements should be taken and recorded in metric notation using a ruler or calipers. All baseline evaluations should be performed as closely as possible to the beginning of treatment and never more than 4 weeks before the beginning of the treatment.

The same method of assessment and the same technique should be used to characterize each identified and reported lesion at baseline and during follow-up. Imaging-based evaluation is preferred to evaluation by clinical examination unless the lesion(s) being followed cannot be imaged but are assessable by clinical exam.

**Clinical lesions:** Clinical lesions will only be considered measurable when they are superficial (e.g., skin nodules and palpable lymph nodes) and  $\geq 10$  mm diameter as assessed using calipers (e.g., skin nodules). In the case of skin lesions, documentation by color photography, including a ruler to estimate the size of the lesion, is recommended.

**Chest x-ray:** Lesions on chest x-ray are acceptable as measurable lesions when they are clearly defined and surrounded by aerated lung. However, CT is preferable.

**Conventional CT and MRI:** This guideline has defined measurability of lesions on CT scan based on the assumption that CT slice thickness is 5 mm or less. If CT scans have slice thickness greater than 5 mm, the minimum size for a measurable lesion should be twice the slice thickness. MRI is also acceptable in certain situations (e.g. for body scans).

Use of MRI remains a complex issue. MRI has excellent contrast, spatial, and temporal resolution; however, there are many image acquisition variables involved in MRI, which greatly impact image quality, lesion conspicuity, and measurement. Furthermore, the availability of MRI is variable globally. As with CT, if an MRI is performed, the technical specifications of the scanning sequences used should be optimized for the evaluation of the

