## 13.4 Response Criteria

### 13.4.1 Evaluation of Target Lesions

**Complete Response (CR):** Disappearance of all target lesions. Any pathological lymph nodes (whether target or non-target) must have reduction in short axis to <10 mm.

**Partial Response (PR):** At least a 30% decrease in the sum of the diameters of target lesions, taking as reference the baseline sum diameters.

**Progressive Disease (PD):** At least a 20% increase in the sum of the diameters of target lesions, taking as reference the smallest sum on study (this includes the baseline sum if that is the smallest on study). In addition to the relative increase of 20%, the sum must also demonstrate an absolute increase of at least 5 mm. (Note: the appearance of one or more new lesions is also considered progression).

**Stable Disease (SD):** Neither sufficient shrinkage to qualify for PR nor sufficient increase to qualify for PD, taking as reference the smallest sum diameters while on study.

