#### For Patients with Non-Measurable Disease (i.e., Non-Target Disease)

Non-Target Lesions	New Lesions	Overall Response
CR	No	CR
Non-CR/non-PD	No	Non-CR/non-PD*
Not all evaluated	No	not evaluated
Unequivocal PD	Yes or No	PD
Any	Yes	PD

\* 'Non-CR/non-PD' is preferred over 'stable disease' for non-target disease since SD is increasingly used as an endpoint for assessment of efficacy in some trials so to assign this category when no lesions can be measured is not advised

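### Inclusion 3 has no short-axis rule for nodes, so a patient can be eligible with no CT target lesion under Section 13.2 and then cannot be scored PR

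*Combined protocol and SAP*

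**What the plan says.** **Eligibility.** Inclusion 3 in Section 3.1 reads "Measurable disease defined as lesions that can be accurately measured in at least one dimension (longest diameter to be recorded) as" 10 mm or more on CT, 20 mm or more on chest x-ray, or 10 mm or more with calipers. It gives no short-axis criterion and does not refer to Section 13.

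**Response assessment.** Section 13.2 opens with a nearly identical general definition and then adds a paragraph on malignant nodes: "a lymph node must be >15 mm in short axis when assessed by CT scan". Small lesions, including nodes of 10 to under 15 mm short axis, "are considered non-measurable disease". Target lesions come only from the measurable set: "All measurable lesions up to a maximum of 2 lesions per organ and 5 lesions in total".

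**Scoring.** Section 13.4.1 defines PR as "At least a 30% decrease in the sum of the diameters of target lesions, taking as reference the baseline sum diameters". For patients without target disease, the table in Section 13.4.3 allows CR, non-CR/non-PD, not evaluated, or PD. It has no PR row.

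**Denominator.** Section 5.4 treats all patients as evaluable for response unless they stop early for listed reasons and have had no disease assessment. Lacking a target lesion is not one of those reasons. Section 14.2 defines the primary endpoint as the proportion with CR or PR.

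**Clinical route.** Section 13.3 states: "Clinical lesions will only be considered measurable when they are superficial (e.g., skin nodules and palpable lymph nodes) and" at least 10 mm by calipers. The same section prefers imaging unless a lesion cannot be imaged.

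**The concern.** A measurable-disease criterion is there to ensure that every enrolled patient can be assessed for the primary endpoint. Here the entry definition and the assessment definition use different axes and different limits for nodes, and nodal disease is common ground for a Stage III to IVB head and neck population.

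A patient who falls between the two definitions counts in the denominator of the CR/PR rate with PR closed off. Any resulting bias in the response rate can only be downward. The same patient could be scored as progressing only through new lesions or unequivocal growth of non-target disease. That also touches the interim review in Section 14.7, which counts RECIST progression at the end of Step One.

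**Working it through.** **1. The two rules applied to one node.** Take a neck node 18 mm long and 12 mm in short axis on CT, in a patient whose primary is not measurable.

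| Question | Section | Answer |
|---|---|---|
| Meets inclusion 3? | 3.1 | Yes: 18 mm is at least 10 mm longest diameter |
| Measurable node on CT? | 13.2 | No: 12 mm short axis lies in the 10 to under 15 mm non-measurable band |
| CT target lesion? | 13.2 | No: targets come only from measurable lesions |
| PR possible? | 13.4.1, 13.4.3 | No: PR needs a target-lesion sum, and the non-target table has no PR row |
| CR possible? | 13.4.2, 13.4.3 | Yes, if all non-target disease disappears and nodes fall below 10 mm short axis |
| Removed from the denominator? | 5.4 | No |

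**2. Does another criterion close the gap?** Section 3.2 excludes "diagnosis of neck nodes with unknown primary", so every patient has a known primary. Nothing requires that primary to be measurable. Section 13.3 advises against endoscopy for objective tumor evaluation, so endoscopic documentation of the primary does not supply a target lesion.

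**3. Does the caliper route close it?** Only in part. A palpable node of at least 10 mm can be measurable under Section 13.3. However, that section prefers imaging when the lesion can be imaged, and Step One response is assessed by CT of the neck (Sections 5.0 and 5.3.2). For a node that is both palpable and visible on CT, Sections 13.2 and 13.3 can give opposite answers, and the protocol does not say which governs.

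**4. Illustration of size, on assumed numbers.** From Section 14.5: N = 24, null rate 17%, alternative 38%, one-sided exact test at 0.05.

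- The critical value is the smallest r with P(X ≥ r | 24, 0.17) ≤ 0.05. For r = 7 the probability is 0.099 and for r = 8 it is 0.039, so r = 8.
- Exact power is P(X ≥ 8 | 24, 0.38) = 74.9%. The plan states more than 80%. A one-sided normal approximation using the null variance gives 80.1%, which may explain that figure. This difference is a separate matter and does not bear on the present point.
- Let k patients have no target lesion and not reach CR, and let the others respond at 38%. The expected rate is 38% × (24 − k)/24, and power is P(X ≥ 8 | 24 − k, 0.38).

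| k (assumed) | Expected rate | Exact power |
|---|---|---|
| 0 | 38.0% | 74.9% |
| 1 | 36.4% | 69.8% |
| 2 | 34.8% | 64.1% |
| 3 | 33.3% | 57.8% |

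The documents give no value for k, and k = 0 is entirely plausible.

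**The case against.** The best reply is that the sections can be read together. Inclusion 3 nearly repeats the general paragraph of Section 13.2, the nodal paragraph qualifies that general rule, and Section 13.1 says nodes are measured by shortest diameter. An investigator working under RECIST 1.1 would probably apply the nodal rule at screening. On that view this is a missing cross-reference. The point has force, but inclusion 3 is written as a complete definition based on longest diameter, and nothing in it directs the reader to Section 13.

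The situation also needs several conditions at once: a primary that is not measurable, no node above the nodal limit on CT, and no lesion accepted by calipers. That stands, and it is why the expected effect is small.

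A reader might infer more than the text supports:

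- *That such a patient certainly has no target lesion.* The caliper route in Section 13.3 may supply one.
- *That such a patient cannot respond.* CR stays available and counts towards the primary endpoint.
- *That the trial loses a stated amount of power.* The values of k above are assumptions, and they treat these patients as certain non-responders.
- *That a node of exactly 15 mm belongs to no category.* Section 13.2 puts all lesions that are not measurable into the non-measurable class, so read literally it falls there.
- *That the strict signs in Section 13.2 are a drafting error.* They differ from the signs in Section 3.1, but an underline lost when the PDF was read would produce the same appearance.

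**Conclusion.** The mismatch between inclusion 3 and Section 13.2 holds for nodes assessed by CT. It lets a patient be enrolled, remain in the response denominator, and be ineligible for PR by construction. Any bias in the primary response rate is downward.

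Its size is unknown and probably small. It is zero if every enrolled patient has another measurable lesion or an accepted caliper measurement. The power figures are an illustration under assumed counts and should not be reported as a finding. This is a modest defect in how the primary endpoint is secured at entry, and it is worth correcting because the correction costs almost nothing.

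**What to change.** - Amend inclusion 3 to require at least one lesion that qualifies as a target lesion under Section 13. Apply the Section 13.2 short-axis rule to nodes assessed by CT, and keep the existing caliper and chest x-ray routes. A rule listing only CT criteria would exclude patients whom Sections 3.1, 13.2 and 13.3 currently accept.
- State in Sections 13.2 and 13.3 which rule governs a node that is both palpable and visible on CT.
- Use the same boundary signs in Sections 3.1 and 13.2.

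For patients already enrolled, the number without a target lesion can be counted from the baseline RECIST form listed in Section 12.0. That count would replace the assumed k.

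The cost is amendment wording. The downside is that an occasional patient with only small nodes and no other measurable lesion would not be enrolled.
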